treatment would give us more than 90% power to detect a significant difference with an α of 0.05 with a 2-sided Student's t-test. The analysis of each individual is very labor intensive and costly but fortunately, significant findings on the establishment of B-cell tolerance can be obtained with a relatively small number of subjects.

Data Management

We will use Johns Hopkins REDCap (Research Electronic Data Capture) [https://projectredcap.org/], a secure web application to collect data, create the study database and access the data for analysis. Study coordinator will enter the data required by the protocol into the Electronic Case Report Forms (CRFs). The PI will assure that the data entered into CRFs are complete and accurate.

Data Quality Assurance

Accurate, consistent, and reliable data will be ensured through the use of standard practices and procedures.

SAFETY REPORTING OF ADVERSE EVENTS ASSESSMENT OF SAFETY

Specification of Safety Variables

Safety assessments will consist of monitoring and reporting adverse events (AEs) and serious adverse events (SAEs) per protocol. This includes all events of death, and any study specific issue of concern.

Adverse Events

An AE is any unfavorable and unintended sign (including an abnormal laboratory finding), symptom, or disease temporally associated with the use of an investigational medicinal product (IMP) or other protocol-imposed intervention, regardless of attribution.

This includes the following:

• AEs not previously observed in the subject that emerge during the protocol-specified AE reporting period, including signs or symptoms associated with multiple sclerosis that were not present prior to the AE reporting period.

• Complications that occur as a result of protocol-mandated interventions (e.g., invasive procedures such as cardiac catheterizations)

• If applicable, AEs that occur prior to assignment of study treatment associated with medication washout, no treatment run-in, or other protocol-mandated intervention.

• Preexisting medical conditions (other than the condition being studied) judged by the investigator to have worsened in severity or frequency or changed in character during the protocol-specified AE reporting period.

Serious Adverse Events

An AE should be classified as an SAE if the following criteria are met:

• It results in death (i.e., the AE actually causes or leads to death).

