• It is life threatening (i.e., the AE, in the view of the investigator, places the subject at immediate risk of death. It does not include an AE that, had it occurred in a more severe form, might have caused death.).

• It requires or prolongs inpatient hospitalization.

• It results in persistent or significant disability/incapacity (i.e., the AE results in substantial disruption of the subject's ability to conduct normal life functions).

• It results in a congenital anomaly/birth defect in a neonate/infant born to a mother exposed to the IMP.

• It is considered a significant medical event by the investigator based on medical judgment (e.g., may jeopardize the subject or may require medical/surgical intervention to prevent one of the outcomes listed above).

METHODS AND TIMING FOR ASSESSING AND RECORDING SAFETY VARIABLES

The investigator is responsible for ensuring that all AEs and SAEs that are observed or reported during the study are collected and reported to appropriate IRB(s), and Genentech, Inc.

Adverse Event Reporting Period

The study period during which AEs and SAEs as described in section J where the patient has been exposed to Genentech product must be reported. Reporting period begins after informed consent is obtained and initiation of study treatment and ends 30 days following the last administration of study treatment or study discontinuation/termination, whichever is earlier. After this period, investigators should only report SAEs that are attributed to prior study treatment.

Assessment of Adverse Events

All AEs and SAEs whether volunteered by the subject, discovered by study personnel during questioning, or detected through physical examination, laboratory test, or other means will be reported appropriately. Each reported AE or SAE will be described by its duration (i.e., start and end dates), regulatory seriousness criteria if applicable, suspected relationship to the ocrelizumab (see following guidance), and actions taken.

To ensure consistency of AE and SAE causality assessments, investigators should apply the following general guideline:

Yes

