There is a plausible temporal relationship between the onset of the AE and administration of the {study drug}, and the AE cannot be readily explained by the subject's clinical state, intercurrent illness, or concomitant therapies; and/or the AE follows a known pattern of response to the ocrelizumab or with similar treatments; and/or the AE abates or resolves upon discontinuation of the ocrelizumab or dose reduction and, if applicable, reappears upon re- challenge.

No

Evidence exists that the AE has an etiology other than the ocrelizumab (e.g., preexisting medical condition, underlying disease, intercurrent illness, or concomitant medication); and/or the AE has no plausible temporal relationship to ocrelizumab administration (e.g., cancer diagnosed 2 days after first dose of study drug).

Expected adverse events are those adverse events that are listed or characterized in the Package Insert (P.I) or current Investigator Brochure (I.B).

Unexpected adverse events are those not listed in the P.I or current I.B or not identified. This includes adverse events for which the specificity or severity is not consistent with the description in the P.I. or I.B. For example, under this definition, hepatic necrosis would be unexpected if the P.I. or I.B. only referred to elevated hepatic enzymes or hepatitis.

PROCEDURES FOR ELICITING, RECORDING, AND REPORTING ADVERSE EVENTS

Eliciting Adverse Events

A consistent methodology for eliciting AEs at all subject evaluation time points should be adopted. Examples of non-directive questions include:

- "How have you felt since your last clinical visit?"
- "Have you had any new or changed health problems since you were last here?"

Specific Instructions for Recording Adverse Events

Investigators should use correct medical terminology/concepts when reporting AEs or SAEs. Avoid colloquialisms and abbreviations.

a. Diagnosis vs. Signs and Symptoms

If known at the time of reporting, a diagnosis should be reported rather than individual signs and symptoms (e.g., record only liver failure or hepatitis rather than jaundice, asterixis, and elevated transaminases). However, if a constellation of signs and/or symptoms cannot be medically characterized as a single diagnosis or syndrome at the time of reporting, it is acceptable to report the information that is currently available. If a diagnosis is subsequently established, it should be reported as follow-up information.

b. Deaths

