All deaths that occur during the protocol-specified AE reporting period (see Section I), regardless of attribution, will be reported to the appropriate parties. When recording a death, the event or condition that caused or contributed to the fatal outcome should be reported as the single medical concept. If the cause of death is unknown and cannot be ascertained at the time of reporting, report "Unexplained Death".

c. Preexisting Medical Conditions

A preexisting medical condition is one that is present at the start of the study. Such conditions should be reported as medical and surgical history. A preexisting medical condition should be re-assessed throughout the trial and reported as an AE or SAE only if the frequency, severity, or character of the condition worsens during the study. When reporting such events, it is important to convey the concept that the preexisting condition has changed by including applicable descriptors (e.g., "more frequent headaches").

d. Hospitalizations for Medical or Surgical Procedures

Any AE that results in hospitalization or prolonged hospitalization should be documented and reported as an SAE. If a subject is hospitalized to undergo a medical or surgical procedure as a result of an AE, the event responsible for the procedure, not the procedure itself, should be reported as the SAE. For example, if a subject is hospitalized to undergo coronary bypass surgery, record the heart condition that necessitated the bypass as the SAE.

Hospitalizations for the following reasons do not require reporting:

• Hospitalization or prolonged hospitalization for diagnostic or elective surgical procedures for preexisting conditions

• Hospitalization or prolonged hospitalization required to allow efficacy measurement for the study or

• Hospitalization or prolonged hospitalization for scheduled therapy of the target disease of the study

e. Assessment of Severity of Adverse Events

The adverse event severity grading scale for the NCI CTCAE (v5.0 Update current versions) will be used for assessing adverse event severity. Below Table should be used for assessing severity for adverse events that are not specifically listed in the NCI CTCAE.

Adverse Event Severity Grading Scale for Events Not Specifically Listed in NCI CTCAE

Grade	Severity
1	Mild; asymptomatic or mild symptoms; clinical or diagnostic observations only; or intervention not indicated

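### The safety reporting rule contradicts itself: all events during the study are reportable, yet the reporting period closes at about month 7 of 30

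*Combined protocol and SAP*

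**What the plan says.** The section on methods and timing for recording safety variables sets the investigator's general duty: "all AEs and SAEs that are observed or reported during the study are collected and reported to appropriate IRB(s), and Genentech, Inc". This sentence has no cut-off before the end of the study and no attribution test.

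The subsection that follows, Adverse Event Reporting Period, ties its period to this requirement: "AEs and SAEs as described in section J where the patient has been exposed to Genentech product must be reported". Item j is the exchange of single case reports with Genentech. The period "ends 30 days following the last administration of study treatment or study discontinuation/termination, whichever is earlier". After it, "investigators should only report SAEs that are attributed to prior study treatment".

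Four other places bear on the point:
- Specification of Safety Variables says of AE and SAE reporting: "This includes all events of death, and any study specific issue of concern".
- On fatal events, item b says: "All deaths that occur during the protocol-specified AE reporting period (see Section I), regardless of attribution, will be reported to the appropriate parties".
- The last bullet under Adverse Events counts the worsening of a preexisting condition if it happens in the reporting period.
- Item c, Preexisting Medical Conditions, makes such worsening reportable if it happens in the course of the study.

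Study Interventions places the second and last course six months after the first. The schedule of events runs to month 30, with side-effects assessments at months 3, 6, 12, 18, 24 and 30.

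**The concern.** Dosing takes up the first six months of a 30-month study. A reporting period tied to the last dose, with the earlier of two dates deciding, therefore ends long before follow-up does. The study's stated deviation from standard care is that infusions stop after two courses, and any consequence of stopping must arise after the second course.

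At stake is whether the safety record is complete and consistent. Take a new non-serious AE at month 12, an SAE at month 20 judged unrelated to ocrelizumab, or an unattributed death at month 24. One sentence tells staff to report it, and another tells them not to. What is on file would depend on which sentence was followed.

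**Working it through.** **When the period closes.** Inputs: last scheduled infusion at month 6 (Study Interventions); 30 days (Adverse Event Reporting Period); last visit at month 30 (schedule of events); 1 month = 30.4375 days.

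- Six months counted from day 1: 6 + 30/30.4375 = month 6.99.
- Six months counted from the second infusion, 14 days later: 6 + 14/30.4375 + 30/30.4375 = month 7.45.

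For a participant who receives both courses and stays on study, this date comes before study discontinuation or termination, so it is the one that applies.

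**What falls after closure.**

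| | Closure 6.99 | Closure 7.45 |
|---|---|---|
| Months left of 30 | 23.01 | 22.55 |
| Share of schedule | 23.01/30 = 76.7% | 22.55/30 = 75.2% |
| Side-effects assessments after closure | 12, 18, 24, 30 (4 of 6) | 12, 18, 24, 30 (4 of 6) |
| Months to next assessment | 12 - 6.99 = 5.01 | 12 - 7.45 = 4.55 |

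The COVID-19 changes allow infusions to be delayed but give no length. Assuming a delay of 1 to 6 months in the second course (from month 6 to month 7 to 12), closure moves to month 7.99 to 12.99. That leaves 22.01 to 17.01 months, or 73% to 57% of the schedule. The gap shrinks but does not close.

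**When stopping infusions can matter.** Stopping cannot have an effect before a further course would have been given. The documents state no interval after the second course. For that date to fall inside the reporting period, the interval would have to be about a month or less, against the six months between the first two courses.

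**The rules side by side, for an event with onset after closure.**

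| Event | Reportable under | Not reportable under |
|---|---|---|
| New non-serious AE | General duty in the methods and timing section | Adverse Event Reporting Period |
| SAE not attributed to treatment | General duty | Adverse Event Reporting Period |
| Unattributed death | Specification of Safety Variables; general duty | Item b gives no duty; Adverse Event Reporting Period |
| Worsening of a preexisting condition | Item c | Last bullet under Adverse Events; Adverse Event Reporting Period, unless an attributed SAE |

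An event that starts inside the period but is first mentioned at month 12 is taken as still reportable. The conflict concerns later onset.

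**The case against.** **A specific rule limits a general one.** The general duty is followed at once by a subsection that sets the timing, and its last sentence is explicit when read alone. The Adverse Events bullets and item b also use the period as a working term. This is the strongest defence. It fails because item c extends reporting over the whole study, and the statement on deaths is unqualified apart from a reference to reporting per protocol. These are also specific provisions, and they point the other way. Nor can one say that collection continues and only onward reporting stops, since the general duty joins the two.

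**A later event may not be an AE by definition.** One bullet covers events "that emerge during the protocol-specified AE reporting period, including signs or symptoms associated with multiple sclerosis". But the bullets are introduced as inclusions, and the core definition above them does not mention the reporting period.

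**The period may cover only the Genentech exchange.** The reference to section J supports this, and the text does not exclude it. IRB reporting would then run on. This stands as a limit on the point, but the general duty names Genentech too, so the conflict over that recipient remains.

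**Little depends on it.** Statistical Methods plans no AE analysis. Return of disease is a secondary outcome and feeds the stop and termination rules. Attributed SAEs, pregnancies within six months after the last dose and lack-of-efficacy reports stay reportable. All of this stands and bounds the consequence.

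**A stronger reading.** A reader might infer that the hospitalisation rule (item d), the Grade 4 and 5 note, the deadline for unrelated SAEs, the post-study item (g) and the instruction "A consistent methodology for eliciting AEs at all subject evaluation time points should be adopted" all contradict the period as well. They do not. The first two classify events. The deadline also serves unrelated SAEs that occur inside the period. Item g asks for attributed SAEs, which the period rule also keeps. Questioning at every visit is needed to find those attributed SAEs.

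**Conclusion.** The rule is wrong as written because it contradicts itself. For a participant dosed on schedule, the reporting period closes at about month 7 to 7.5. About 75-77% of the 30-month schedule and four of six side-effects assessments come later. For that time the protocol gives two answers on non-serious AEs, unattributed SAEs, unattributed deaths and worsening of preexisting conditions. If the period limits only the exchange with Genentech, the conflict narrows to that recipient.

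The figures assume that both courses are given on time and that the participant stays to month 30.

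A reader might go further and infer that participants are unmonitored after month 7, or that the trial's results are biased. The documents support neither. Side effects are assessed to month 30, and no planned endpoint analysis uses the AE reports. The defect lies in what must be recorded and reported.

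**What to change.** Reconcile Specification of Safety Variables, the Adverse Events bullets, the general duty, Adverse Event Reporting Period, and items b and c, so that:
- AEs, SAEs and deaths are recorded and reported to the IRB through the participant's last study visit, or 30 days after the last study treatment if that is later;
- the rule limiting reports to attributed SAEs applies only after that point;
- if the shorter period is meant only for the exchange with Genentech in item j, the text says so and the general duty is worded to match;
- the text states how a relapse already captured as an outcome is recorded, because new MS signs and symptoms count as AEs and could otherwise be reported twice.

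This changes wording only, since the visits and side-effects assessments are already scheduled. The cost is some additional AE forms for 10 patients.
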